Number of patients in each group in whom all parameters are normal at the end of induction for:

- Liver function
- Cholesterol, triglycerides, low and high density lipoproteins, apoprotein A1, B and A1:B ratio
- Fasting glucose and insulin (HOMA)

4 STUDY DESIGN and METHODS of DATA COLLECTION AND DATA ANALYIS

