4.1 Identification of patients and enrolment process (see Figure 1)

At 10-11 years clinicians should, as part of normal clinical practice, assess the need for pubertal induction by measuring the hormone follicle-stimulating hormone (FSH), levels of >10 IU/L indicating a degree of primary ovarian failure necessitating estrogen replacement.

Clinicians from European countries and beyond who wish to participate in the study will counsel the families of girls requiring pubertal induction as to the options. These include either of the oral and transdermal regimens agreed and recommended by the TSWG of ESPE; and alternative regimens.

This is an open, non-randomised study comparing two regimens which are regarded as best practice. Clinicians will be asked to help families make an informed choice regarding either or neither of the oral or transdermal regimens recommended by TSWG. Choice will depend partly on the availability of the recommended transdermal or oral 17β -estradiol preparations, but clinicians are entitled to request appropriate, treatment from their hospitals and pharmacies which comply with Cincinnati and UK guidelines [13,14]. In the event of a family choosing either of the TSWG-recommended regimens, written informed consent and assent will be requested by the clinician for participation in the study and the European central registry will be contacted.

This consent is for anonymised data (with the exception of date of birth, which is required for analysis) before, during and after pubertal induction to be sent to the designated European centre and entered into an independent ESPE-approved database under the supervision of an ESPE TSWG member trained in Good Clinical Practice.

In the UK, NHS Research Ethics Committee (REC) & Research and Development (R&D)/HRA approvals will be sought, enabling participating centres to recruit and enroll patients into the study.

Outside the UK, participating centers will need to follow their national regulatory procedure and gain ethical approval for patients and families to give written consent.

Since the proposal is not a randomised clinical trial, but an observational cohort study it should not need to be registered as the former. Any medications given for pubertal induction would be prescribed and funded in the usual way for the country concerned.

4.2 Age, duration and protocols for oral and transdermal 17β-estradiol induction of puberty in TS

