4.5 Data collection before and during pubertal induction

Table 4 shows the recommended information to be collected before, during and at the end of pubertal induction, and until adult height, i.e. height velocity < 2 cm/year.

TABLE 4 Recommended measurements before, during and at the end of pubertal induction with either transdermal or oral 17-β
estradiol grouped according to priority – essential and desirable.

Variable	Before induction (± 6 months)		End of Years 1 & 2	End of Year 3	Comment	
ESSENTIAL	(2 o montho)	visito				
Karyotype	X				From time of diagnosis	
Auxology Height (cm)	x	x	x	х		
Weight (kg)	X	Х	X	Х	 Previous growth data will be requested, to enable calculation of a) height velocity, using 12 (±1) month interval, during previous year; and GH responsiveness – derived from height/weight status one year prior to, at the start of, and one year after starting GH. 	
Height velocity (cm/yr)	X		X	Х		
Measured parental heights (where available)	X					
Breast and pubic hair stage (1-5)	X	Х	X	Х		
Systolic & diastolic blood pressure (mm Hg)	Х	Х	Х	Х	Lowest of three consecutive readings using Dinamap V100 or similar device	
Adherence to treatment		X	Х	Х	Scored according to estrogen doses missed per month as good (≤ 2) moderate (≤ 4) and poor (> 4)	
Adverse events/illness		Х	Х	Х	All adverse events (e.g. injury, intercurrent infection) irrespective of relevance to growth and puberty	
FSH, LH	X			Х		
Free T4 and TSH	Х			Х		
Liver function	Х		Х	Х		
HbA1c	Х			Х		
Concurrent treatment	Х	Х	Х	Х	GH, L-T4, Oxandrolone	
DESIRABLE	1					
Final adult height					Measurement once height velocity < 2cm/year	
Bone age	Х		Х	Х	Assessed using 'BoneXpert', where available	
Sitting height	X	X	Х	Х		
Echocardiography	X			Х	Including measurement of aortic size index	
Pelvic ultrasound	Х		X	Х	Uterine length, shape and volume, endometrial thickness	
DXA BMC	Х			Х	Hip and lumbar spine z-score Total body BMD	
Fasting lipid profile	Х			Х	Cholesterol, triglycerides, low and high-density lipoproteins	
Coagulation studies	X			Х		
Serum estradiol	X			Х	Beginning of Year 4 (see Table 2)	
Serum IGF-I	X		Х	Х	Keep +1.5 -2.5 SD of reference range	
24h continuous ambulatory blood pressure	X			Х		
Fasting blood glucose and insulin	Х			Х		

Abbreviations

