FSH = follicle stimulating hormone; LH = luteinising hormone; fT4 = free thyroxine; TSH = thyroid stimulating hormone; DXA = dual X-ray absorptiometry; BMC = bone mineral content; BMD = bone mineral density; GH = growth hormone; L-T4 = levo-thyroxine. *4-monthly visits are recommended; however 3-6 monthly may be more suitable for some participating centres.

It should be noted that measurements such as height, weight, pubertal stage and blood pressure are marked as 'essential' and are within the scope of any paediatric service caring for girls with TS. By contrast, 'desirable' measures should be undertaken at the clinician's discretion, and take account of the resources available in the participating centre.

Since height gain during induction is the agreed primary outcome measure, previous height and weight data from one year before, at the time of and one year after the start of GH treatment and at least yearly thereafter, together with GH dose and possible oxandrolone treatment, are required to assess GH responsiveness [29,30].

Karyotype (normally available from time of diagnosis) is essential information.

At each visit, measurement of height, weight, blood pressure, pubertal stage, adherence (scored according to the number of estrogen doses estimated by the family to have been missed per month), recording of adverse events, and concurrent treatment are required.

Note that the family will be asked at each visit about **any** adverse events including minor injury, intercurrent infection, middle ear problems and gastrointestinal symptoms, and summarised at the end of each year by the clinician.

Annual biochemistry for thyroid function and liver function, FSH, LH and estradiol levels will be carried out as part of normal clinical practice.

Echocardiogram to define the anatomy of the heart and great vessels, with measurement of aortic root diameter at the annulus, and aortic size index (aortic root diameter divided by body surface area), is recommended before and at the end of induction.

Pelvic ultrasound, measuring uterine length, fundo-cervical ratio, uterine shape (infantile, cylindrical and pubertal) and endometrial thickness are also recommended before and after induction.

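### The metabolic outcome counts girls with all results normal at the end of induction, without a denominator or pre-induction value, so unequal testing or baseline status can distort the comparison

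*Protocol*

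**What the plan says.** The last item of Table 1 (Protocol, section 3.2) is the metabolic profile. Its measure is "Number of patients in each group in whom all parameters are normal at the end of induction for" three domains: liver function; "Cholesterol, triglycerides, low and high density lipoproteins, apoprotein A1, B and A1:B ratio"; and glucose with insulin, measured fasting. It is not plain whether all parameters must be normal within each domain or across all three.

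Table 4 (section 4.5) sets the collection. "Liver function" is in the essential block: before induction, at the end of Years 1 and 2, and at the end of Year 3. "Fasting lipid profile" and "Fasting blood glucose and insulin" are in the desirable block: before induction and at the end of Year 3. The comment on the lipid row names cholesterol, triglycerides and the low- and high-density lipoproteins, but no apoproteins. The text below the table adds: "desirable' measures should be undertaken at the clinician's discretion, and take account of the resources available in the participating centre".

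Section 4.1 makes the study open and non-randomised. On the regimen taken it says: "Choice will depend partly on the availability of the recommended transdermal or oral 17β -estradiol preparations". It adds that clinicians may ask their hospitals and pharmacies for suitable treatment.

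Section 4.6 plans a description of baseline differences, propensity score matching, and, for each outcome, regression on confounders selected with causal graphs. Its example confounders are karyotype, parental height, starting height, growth hormone history and response, and oxandrolone. No metabolic value is among them.

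**The concern.** A count per group is the number tested multiplied by the proportion normal. Only the second factor says anything about the regimen. Nothing in the protocol makes the first factor equal between arms for the optional tests. The target of 84 per arm refers to girls completing the three-year induction, not to girls with a fasting sample.

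The definition also looks only at the end. A girl with an abnormal result before any estradiol counts against whichever regimen she takes, although a pre-induction sample is scheduled. Without randomisation, similar baselines cannot be assumed. Elsewhere Table 1 gives dropout as a percentage, and gives height SDS, the aortic measures and bone density as changes, so the metabolic item is out of step with its neighbours.

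At stake is whether the metabolic comparison of oral with transdermal estradiol can be interpreted. The primary outcome is not affected.

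**Working it through.** **The plan's own figures.** The protocol gives none for the metabolic outcome. Its sample size concerns height gain: 21/(2.5/3.5)² = 41.2, or 21/0.71² = 41.7 with the rounded effect size. Either rounds up to the stated 42, which is doubled to 84. I use 84 below only as the largest number that could be tested in an arm at target.

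**Step 1: numbers tested.** Expected count = number tested × proportion normal. The numbers tested and the proportions are assumptions. With 75% normal on transdermal and 60% on oral:

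| Tested, transdermal | Tested, oral | Normal, transdermal | Normal, oral | Count favours |
|---|---|---|---|---|
| 84 | 84 | 63.0 | 50.4 | transdermal |
| 60 | 84 | 45.0 | 50.4 | oral |
| 42 | 84 | 31.5 | 50.4 | oral |
| 84 | 50 | 63.0 | 30.0 | transdermal |

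The proportion favours transdermal in every row. In the last row the direction is right but the size is not: 63.0/30.0 = 2.1, against a true ratio of 0.75/0.60 = 1.25.

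The count reverses when (transdermal tested)/(oral tested) is below (proportion normal, oral)/(proportion normal, transdermal):

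- 75% versus 60%: 0.60/0.75 = 0.80
- 70% versus 60%: 0.60/0.70 = 0.86
- 80% versus 60%: 0.60/0.80 = 0.75

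With no difference at all (70% normal in both arms), testing 42 against 84 gives 29.4 against 58.8, a twofold gap produced by testing alone.

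**Step 2: baseline.** Suppose all 84 are tested in each arm. Transdermal goes from 60% to 70% normal (50.4 to 58.8 girls), and oral from 85% to 75% (71.4 to 63.0 girls). The end count favours oral, 63.0 to 58.8, although transdermal gained 10 percentage points and oral lost 10. Because testing is equal here, a proportion at the end, 75% to 70%, would mislead in the same way. A denominator alone does not cure this part.

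**Step 3: Table 1 against Table 4.** Table 1 requires apoproteins A1 and B and their ratio to be normal. The Table 4 lipid row does not list them. A girl tested exactly as that row describes could not be classified on the full Table 1 lipid list.

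**The case against.** The strongest reply is that Table 1 lists outcomes, not estimators. Section 4.6 promises regression for each outcome, and a regression of a yes/no indicator works on individual girls, so it carries its own denominator. This stands in part: done that way, the reversal in Step 1 need not occur. But the text of Table 1 is a number per group, and section 4.6 does not redefine it. Section 4.6 also names no baseline metabolic value, and regression on an end-only, all-normal indicator cannot recover how far any analyte moved.

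A second reply is that classing results as normal or abnormal is a sensible answer to differences between laboratories. It is a fair reason to keep such a summary, but not for leaving out the earlier sample. For bone density, section 4.5 meets differing equipment by using each girl's own change.

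Third, this item comes last in a long secondary list, and neither the synopsis nor the opening text of section 3.2 names it among the secondary outcomes. That limits its weight.

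A reader might infer more than the documents support:

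- That the numbers tested will differ by arm. The protocol never links product availability to testing resources; they may differ.
- That the result will point the wrong way. That depends on assumed rates.
- That lipid fractions move in opposite directions by route and cancel in the composite. The documents say nothing of this.
- That a missing HOMA cut-off, or a missing rule for partly tested girls, is an error. Such detail commonly belongs in an analysis plan.

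**Conclusion.** The point holds as a weakness in how a secondary outcome is defined. The count has no denominator and omits a pre-induction value that is scheduled for most of the listed parameters, in a study where arms are chosen and two of the three domains are tested at discretion.

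Under the assumed rates, the order reverses once transdermal testing falls below 75% to 86% of oral testing. Baseline differences can reverse it even with equal testing. Both are possibilities: with equal numbers tested and similar baselines, count and proportion agree. Liver function, as an essential test, is less exposed to the testing problem, but its end-only definition has the same baseline gap.

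**What to change.** Reword the metabolic item in Table 1 as the difference between regimens in each analyte at the end of induction, treated as a continuous value and adjusted for the girl's own pre-induction value, within the confounder models of section 4.6. Report the numbers tested at each time by arm.

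If a normal/abnormal summary is kept, give it per domain as a proportion of girls tested, adjusted for baseline status.

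Reconcile the apoproteins: either add them to the Table 4 lipid row or remove them from Table 1.

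The cost is a change of wording and a little more analysis. Most samples are already scheduled; apoproteins would be an added test if they are kept. The drawback is that the adjusted analysis is limited to girls sampled at both times. For the optional tests this is a selected subset, so the numbers tested must be shown beside the result.

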4.1 Identification of patients and enrolment process (see Figure 1)

At 10-11 years clinicians should, as part of normal clinical practice, assess the need for pubertal induction by measuring the hormone follicle-stimulating hormone (FSH), levels of >10 IU/L indicating a degree of primary ovarian failure necessitating estrogen replacement.

Clinicians from European countries and beyond who wish to participate in the study will counsel the families of girls requiring pubertal induction as to the options. These include either of the oral and transdermal regimens agreed and recommended by the TSWG of ESPE; and alternative regimens.

This is an open, non-randomised study comparing two regimens which are regarded as best practice. Clinicians will be asked to help families make an informed choice regarding either or neither of the oral or transdermal regimens recommended by TSWG. Choice will depend partly on the availability of the recommended transdermal or oral 17β -estradiol preparations, but clinicians are entitled to request appropriate, treatment from their hospitals and pharmacies which comply with Cincinnati and UK guidelines [13,14]. In the event of a family choosing either of the TSWG-recommended regimens, written informed consent and assent will be requested by the clinician for participation in the study and the European central registry will be contacted.

This consent is for anonymised data (with the exception of date of birth, which is required for analysis) before, during and after pubertal induction to be sent to the designated European centre and entered into an independent ESPE-approved database under the supervision of an ESPE TSWG member trained in Good Clinical Practice.

In the UK, NHS Research Ethics Committee (REC) & Research and Development (R&D)/HRA approvals will be sought, enabling participating centres to recruit and enroll patients into the study.

Outside the UK, participating centers will need to follow their national regulatory procedure and gain ethical approval for patients and families to give written consent.

Since the proposal is not a randomised clinical trial, but an observational cohort study it should not need to be registered as the former. Any medications given for pubertal induction would be prescribed and funded in the usual way for the country concerned.

4.2 Age, duration and protocols for oral and transdermal 17β-estradiol induction of puberty in TS

Induction of puberty will be from 11 years. Specific age of beginning induction, and duration of induction are at the discretion of the clinician in consultation with the family. Initiation of treatment in eligible patients should normally begin at between 11-12 years, consistent with the Cincinnati and UK guidelines [13,14]. Pubertal induction should normally be carried out over a 3-year period. However, a later induction age will be necessary in girls presenting >12 years. Also, a faster induction period (e.g. 2 years) should be considered in girls who are older (e.g. >14 years) at the time of starting induction due to late diagnosis.

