3 RESEARCH QUESTION/AIM(S)

Research question: Is transdermal 17β-estradiol induction superior to oral induction in terms of key parameters including pubertal height gain and adult height, cardiac (e.g. blood pressure), uterine and bone health, and in acceptability?

Study hypothesis: Induction of puberty using transdermal 17β -E2 will result in better outcomes for some key parameters.

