3.2 Outcomes

The primary outcome measure is height gain in cm during the pubertal induction period, since this can be accurately determined in the context of an international framework. Secondary outcome measures include final adult height, systolic blood pressure, aortic root diameter, uterine size and shape, bone mineral density, adherence and dropout rate.

Table 1 Outcome measures to be analysed at the end of pubertal induction in girls with Turner syndrome using either an oral (see Tables 2a and 2b) or transdermal (see Tables 3a and 3b) 17- β estradiol regimen approved by the Turner Syndrome Working Group of ESPE.

Induction period is normally 3 years (plus 6 months for very short girls), exceptionally 2 years for girls presenting late (e.g. >14 years), minimum follow up is during induction period but where possible, follow up is to final adult height.

Primary outcome measure

Pubertal height gain, i.e. increase in height in centimetres during the (usually) 3-year pubertal induction period

Secondary outcome measures

- Final adult height in centimetres & population-specific SDS
- Change in population-specific height SDS between start and end of pubertal induction
- Breast development (clinical assessment)
 - Tanner B4-5 reached
 - Satisfactory breast shape (ie not tubular, no overdevelopment of areolae) according to attending clinician (graded as satisfactory or unsatisfactory)
- Cardiovascular health
 - Systolic & diastolic blood pressure at the end of induction (lowest of three readings or mean values if recorded by ambulatory 24-hour blood pressure monitoring
 - Change in aortic root diameter and aortic size index between start and completion of induction
- Patient satisfaction; adherence/compliance with treatment
 - Percentage drop-outs from either regimen
 - Average of good, reasonable and poor rating with adherence during pubertal induction (3 years ± X months)
 - Patient satisfaction with shape and size of breast (scoring 1-5 where 5=best)
 - Patient satisfaction with mode of administration (scoring 1-5 where 5=best)
- Uterine health and sex hormone profile at the end of induction
 - Uterine length and volume, endometrial thickness
 - Uterine shape and fundo-cervical ratio
 - LH and FSH
 - Serum 17-β estradiol

- Skeletal age and bone health
 - Change in bone age/chronological age per year
 - Change in size-adjusted whole body lumbar spine and hip bone mineral areal density (BMAD) (z-score) before and after induction
- Metabolic profile

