4.6 Data analysis

When the target number of patients has been enrolled (see below), and a sufficient number (84 in each arm) have completed the full 3-year induction, the following analyses between the transdermal and oral groups will be conducted:

- Demographics of patients choosing oral or transdermal estradiol preparations, differences at baseline
- Numbers of patients in each treatment arm, their centres and countries
- Adherence to each of the treatment arms including % of dropouts
- Propensity score matching to reduce bias due to confounding factors e.g. 45,X karyotype, midparental height, height at the beginning of pubertal induction, duration of prior GH treatment, GH responsiveness and treatment or not with oxandrolone.
- Use of Directed Acyclic Graphs to establish the minimally sufficient set of confounders for each outcome parameter, entering these into multivariable regression models

The minority of girls undergoing a 2-year induction will be analysed separately and their outcomes compared with the majority of girls undergoing the full three-year induction

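### Routes available to each girl and the reason for her choice are not listed for collection, so the comparison of acceptability between routes mixes route with preference and availability

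*Protocol*

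**What the plan says.** All references are to the Protocol.

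- **Question.** Section 3 asks whether transdermal induction is superior on several parameters, among them "cardiac (e.g. blood pressure), uterine and bone health, and in acceptability". The synopsis repeats this and ties acceptability to adherence. Section 1 names acceptability and adherence as evidence gaps.
- **Outcomes.** Table 1 in section 3.2 lists "Patient satisfaction with mode of administration (scoring 1-5 where 5=best"), an averaged adherence rating, and "Percentage drop-outs from either regimen".
- **Counselling.** Section 4.1: "Clinicians will be asked to help families make an informed choice regarding either or neither of the oral or transdermal regimens". Alternative regimens are also discussed.
- **Entry.** Section 4.1: "In the event of a family choosing either of the TSWG-recommended regimens, written informed consent and assent will be requested". A family choosing neither regimen is not enrolled, and no count of such families is planned.
- **Constraint.** Section 4.1: "Choice will depend partly on the availability of the recommended transdermal or oral 17β -estradiol preparations". The sentence goes on to say that clinicians may request guideline-compliant treatment from their hospitals and pharmacies.
- **Data.** Table 4 in section 4.5, and the text that expands on it, contain no item for routes available, preference, or reason for choice.
- **Analysis.** Section 4.6 plans "Demographics of patients choosing oral or transdermal estradiol preparations, differences at baseline", patient numbers by arm, centre and country, propensity score matching, and regression with confounders chosen by a causal diagram for each outcome. The confounders it names all concern growth.

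**The concern.** A girl rates, adheres to, or abandons a route that her family preferred or that was the only one obtainable. These are different situations, and each arm may hold them in a different proportion. If girls without a real choice are less satisfied or stop more often, the arm with more of them looks worse whatever the merits of the route. Nothing listed for collection separates the two kinds of girl, so the proportions can be neither reported nor adjusted for.

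At stake is the comparative acceptability claim. A later analysis plan could not repair the gap, because it cannot analyse an item that was not collected, and a family's reason for choosing is hard to reconstruct after a three-year induction.

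**Working it through.** **1. The plan's own figure.** No size is given for acceptability. The only calculation (section 6.2) is for height gain: n = 21/f² with f = 2.5/3.5 gives 41.2, rounded up to 42 per arm and doubled to 84. It reproduces. It does not bear on this point, except that 84 per arm is used below as the group size.

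**2. Can availability differ between routes?** Section 4.2.1 says that oral doses below 0.25 mg daily must be prepared by a pharmacy. The Year 1 figure in Table 2a is 5 microgram/kg/day, and 0.25 mg ÷ 5 microgram/kg = 50 kg. On the protocol's own figures, every girl under 50 kg needs pharmacy preparation for the oral route in Year 1. Local capacity can therefore limit one route and not the other, and can do so for one girl and not another in the same centre.

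**3. Can the planned analysis separate availability from route?** Centre and country are recorded and can enter a model. A centre with girls in both arms evidently had both routes in use. A centre with girls in one arm only may have lacked the other route, or its clinicians or families may simply have favoured one; the recorded data cannot tell which. No listed variable gives an individual girl's options or reason.

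**4. Illustration of size.** None of the inputs in this step except 84 per arm comes from the protocol. Assume no true route effect, SD 1 on the 1-5 scale, and girls with a free choice scoring 0.5 to 1.0 points higher than girls with one route only.

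Spurious difference = gap × (free-choice share, transdermal − free-choice share, oral); SE = √(2/84) = 0.154.

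| Free choice, transdermal / oral | Gap 0.5 | Gap 1.0 | Chance of p < 0.05 |
|---|---|---|---|
| 90% / 90% | 0.00 | 0.00 | 5% |
| 90% / 80% | 0.05 | 0.10 | 6% to 10% |
| 90% / 60% | 0.15 | 0.30 | 16% to 49% |
| 90% / 40% | 0.25 | 0.50 | 37% to 90% |
| 60% / 90% | −0.15 | −0.30 | 16% to 49% |

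For drop-out, assume 5% with free choice and 20% without:

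- Transdermal, 90% free: 0.9 × 5% + 0.1 × 20% = 6.5%.
- Oral, 80% free: 0.8 × 5% + 0.2 × 20% = 8.0%, a spurious difference of 1.5 percentage points.
- Oral, 40% free: 0.4 × 5% + 0.6 × 20% = 14.0%, a spurious difference of 7.5 percentage points.
- With the shares at 60% / 90% the difference is 4.5 percentage points in the other direction.

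The calculation shows that the answer turns on a share that the protocol does not plan to record. It does not show that the bias exists, or which way it would run.

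**The case against.** The strongest case against has five parts.

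- **Self-selection is declared.** Sections 1 and 4.1 call the study non-randomised, and section 1 places it among patient preference trials. This stands, and the point does not ask for randomisation. But a preference design needs a record of preference to interpret its results.
- **Suitable preparations are a prerequisite.** The synopsis mentions both tablets and patches, and section 6.3 makes availability a condition of taking part. This makes a large share of girls without choice less likely. It does not remove the constraint, since section 4.1 still expects availability to influence choice.
- **Centre and country are recorded, and the confounder list is only illustrative.** This stands as a partial remedy for supply. It does not reach individual options or reasons.
- **Table 4 is not exhaustive.** The satisfaction scores are outcomes in Table 1 but do not appear in Table 4, the enrolment figure is not shown, and the appendices are still to be written. So the supportable statement is that the protocol does not list these items, not that no form will hold them.
- **Adherence is also an acceptability measure**, scored from missed doses at each visit. It is compared between the same self-chosen groups, so the same difficulty applies.

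Two stronger readings are tempting. A reader might infer that families declining one regimen are lost, and uptake with them. That is not so: a family that declines one and takes the other is enrolled, and section 4.6 reports numbers by arm and centre. Only the families choosing neither, and uptake among girls who had both routes available, are missing. A reader might also infer that both arms must score high and that the comparison says nothing. The documents do not show this; liking a route at the outset does not fix satisfaction after three years of use.

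**Conclusion.** The point holds in a limited form. Entry follows choice, choice depends partly on supply, and the protocol lists no item for routes available or reason for choice. The comparison of satisfaction, adherence and drop-out between routes therefore mixes the effect of route with preference and availability, and the planned adjustment has at best a centre-level proxy.

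Size and direction are unknown. The illustrative 0.05 to 0.50 points and 1.5 to 7.5 percentage points rest wholly on assumed inputs, vanish when free choice is equally common in both arms, and change sign when the imbalance does. It would be too strong to say that acceptability cannot be studied: results within each chosen route remain valid descriptively, and uptake by arm and centre will be known. The limit falls on the claim that one route is more acceptable than the other. Only secondary outcomes are affected.

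**What to change.** Before recruitment, add two items to the essential baseline rows of Table 4:

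1. Routes available for this girl: oral, transdermal, or both.
2. Main reason for the choice: girl or family preference, clinician advice, availability, or medical reason.

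In section 4.6, state that uptake will be reported among girls with both routes available; that satisfaction, adherence and drop-out will be presented separately for girls with and without both routes available; and that any claim of superior acceptability will be limited accordingly. Even where both routes were available the groups remain self-chosen, so the wording should stay cautious. An anonymous centre count of eligible girls counselled, including those choosing neither, is optional.

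Cost: two tick-box items at enrolment and a narrower acceptability claim. No visit, test or patient is added. The group without both routes may be small: at a 10% share it would be about 8 of 84 girls per arm (0.1 × 84 = 8.4), so its results would be descriptive.
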